2.3. Preliminary Studies

Preliminary data obtained in the Baby Bottle study points to an unintentional overfeeding of formula fed infants. From 2012-2013 we conducted the Baby Bottle study at PBRC (NCT01762631). The purpose of the baby bottle study was to validate the remote food photography method (RFPM) for estimating energy intake for formula-fed infants. To this end, we recruited 53 men and women aged 18-80 to prepare bottles of infant formula and take photographs of the bottles simultaneously for the RFPM. The subjects were self-identified as caregivers, that is an individual who had prepared a bottle of infant formula in the past year or non-caregivers. Subjects completed two visits approximately one-week apart and prepared three bottles measuring 2fl oz, 4 fl oz, 6 fl oz and 8 fl oz, such that two trials were conducted at Visit 1 and the final trial was conducted at visit 2. The gram weights recommended for each serving of infant formula is shown in **Figure 1**, alongside the mean \pm se of actual gram weights of servings prepared by the study subjects. Of the 636 bottles prepared, 607 or 95% contained significantly more infant formula powder (by weight) than what was recommended on the package label ($p<.0001$). This finding was

Figure 1. Actual vs. recommended scoop weights

evident for each bottle size which is suggested for infant feeding from birth until 12 months of age and averaged $11 \pm 0.6\%$ (range: -24 to +140%) over-scooping across all bottles. The caloric density of a standard scoop of infant formula is 20 kcal/fl oz and therefore with this unintentional over-scooping the prepared bottles of formula had a caloric density of 22 kcal/fl oz, the caloric density often prescribed to premature infants to accelerate infant growth rate [16]. While this error may appear to be marginal for a single bottle, the error was consistent across

Infant Age	% Overfed/ meal	Energy Intake Kcal/day	Overfed (kcal/d)	Overfed (kcal/wk)
Newborn	11	350	39	273
2 months	11	480	53	371
4 months	11	500	55	385
6 months	11	590	65	455

trials. We can therefore assume that the unintentional over-scooping is consistent within an individual and the overfeeding of the infant would then compound throughout the day as multiple bottles are consumed.

These data are summarized in **Table 1**. For each bottle size the additional

formula added to each bottle, would result in an almost entire day of additional energy intake per week.

[figure not shown]
Furthermore, there was no difference between caregivers and non-caregivers which points to a fundamental error in understanding the package instructions.

3. RESEARCH PLAN: PHASE 1

The proposed study is divided into two phases. Phase I will utilize qualitative data gathered from focus groups to direct the modification of infant formula manufacturer preparation instructions to enhance user understanding and accuracy.

In collaboration with the LA CaTS Health Literacy Core, the health literacy elements of infant formula preparation instructions will be assessed (**Figure 2**).

Initial modifications to the manufacturer instructions will be made to increase reading ease and ability to understand and act on instructions. Tools used to assess the health literacy elements and to inform necessary modifications to the standard instructions include the Patient Education Materials Assessment Tool (PEMAT) [17], Ensuring Quality Information for Patients (EQUIP) [18], and the Health Literacy INDEX [19]. These literacy tools encourage the use of plain language, statement of a clear purpose, specific concrete instructions, use of short sentences, use of pictures to clarify message, clear layout, use of headings, chunking of related information, and audience appropriateness. Directed by the health literacy assessment, we will modify the manufacturer infant formula preparation instructions to decrease the level of health literacy required to properly prepare a bottle of formula. The instructions will be modified to be easier to read and navigate. The aim is to increase the participant's ability to understand the words and measurements and increase their ability to properly act on the instructions. The modified instructions will then be presented to focus groups in a stepwise fashion to continually improve consumer comprehension of the instructions and until feedback from the focus groups is completely addressed.

3.1. Study Population

Up to 40 individuals will be recruited to participate in focus groups at Pennington Biomedical Research Center. Approximately six focus groups (each with 5-10 participants) will be conducted at the PBRC Demonstration Kitchen over the course of approximately 3 months. Focus group participants will be matched based on demographic representation (i.e. level of education, household income, gender, and relation to infants) to encourage equal participation of focus group attendees. A primary caregiver is defined as an individual who has routinely cared for an infant in the last year for more than 12 hours per day. Secondary caregiver is defined as

an individual who has routinely cared for an infant in the last year for less than 12 hours per day. A non-caregiver is an individual who has not routinely cared for an infant in the last year.

3.1.1. Eligibility Criteria

Participants are eligible to participate in this study if they are:

- ≥18 years of age
- Willing to participate in 1 focus group visit at Pennington Biomedical Research Center
- Willing to disclose level of education, household income, gender, and relation to infants (i.e. primary caregiver, secondary caregiver, or non-caregiver)
- English speaking

3.1.2. Exclusion Criteria

Participants are ineligible to participate in this study if they are:

- <18 years of age
- Not willing to participate in 1 focus group visit at Pennington Biomedical Research Center
- Not willing to disclose level of education, household income, gender, and relation to infants (i.e. primary caregiver, secondary caregiver, or non-caregiver)
- Non-English speaking

3.2. Recruitment

Potential participants will be recruited from within PBRC and the Greater Baton Rouge area via Institutional Review Board (IRB) approved posters, flyers and advertisements posted on the PBRC website (<http://www.pbrc.edu/clinicaltrials>) and through PBRC approved social media outlets including but not limited to Facebook, blogs, and Craigslist. In addition to recruitment in the community, the Reproductive Endocrinology and Women’s Health Laboratory has successfully recruited participants for pregnancy, breastfeeding, and women’s health studies through partnerships with Baton Rouge General and Ochsner OB/GYNs and local Women, Infants, and Children (WIC) clinics. Referrals from these collaborators will also be used in recruitment efforts.

3.3. Study Screening

Interested participants will complete initial screening via phone or the online webscreener survey. Interested participants may contact study staff for study description and basic eligibility details via phone or email correspondence. Participants not meeting these basic criteria from the webscreener will be excluded. All eligible volunteers will be assigned a unique study ID number and referred to study staff for study specific screening and focus group scheduling.

3.4. Assessment Schedule and Procedures

Potential participants will complete screening to determine eligibility prior to enrollment. Interested and eligible participants will be scheduled for a focus group visit. At the beginning of the focus group visit, participants will be provided the Whoa Baby Phase 1 informed consent and HIPAA authorization for review and completion. After signing the Whoa Baby Phase 1 informed consent and HIPAA authorization, participants will complete several procedures and participate in focus group discussion at the focus group visit. See **Table 2**, Schedule of Procedures.

TABLE 2. Schedule of Procedures

Visit Assessment	Focus Group Visit
Informed Consent (Adult)	X
Height	X
Weight	X
Individual Interview	X
Health Literacy Assessment via Interview	X
Infant Formula Preparation	X
Focus Group Discussion	X

3.4.1. Focus Group Visit

When an individual arrives to the assigned focus group visit at the PBRC Demonstration Kitchen, the Whoa Baby Phase 1 informed consent will be provided for reading and review. If the participant agrees, the participant will sign the consent prior to the initiation of study procedures. After signing the informed consent, study procedures will be completed as part of the focus group visit. Height and non-fasting body weight will be measured by trained study staff. Before focus group discussion, individuals will be asked (one participant at a time) to go to a different room for the individual structured interview for health literacy assessment and the infant formula preparation procedure. After all participants have completed the individual, structured interviews, infant formula preparation, and anthropometric assessments, the focus group discussion will be completed where the focus group will elicit barriers and facilitators to infant formula using standard package instructions and provide recommendations for improvement of standard infant formula preparation instructions to enhance readability and improve understanding.

3.5. Measures and Outcome Assessments

3.5.1. Anthropometrics

Height and body weight will be measured using standard procedures of PBRC. Non-fasting body weight will be recorded. Body mass index (BMI) will then be calculated from the recorded height and body weight. BMI will be computed as a cohort demographic characteristic to ensure that focus group population is representative of the general population in the Baton Rouge area.

[figure not shown]
3.5.2. Individual Interview

1. **General information:** A research assistant will conduct a structured interview with participants to collect general information (e.g. age, race, income, education, experience with infant formula preparation, number of children, caregiver status, etc.), experience with infant formula preparation, and relation to infants.
2. **Health Literacy Assessment:** Health literacy and numeracy skills will be assessed through structured interview. The following assessments will be completed as part of the health literacy assessment.
 - a. *Rapid Estimate of Adult Literacy in Medicine (REALM-SF):* The REALM-SF [20] asks participants to read medical terms aloud.
 - b. *Newest Vital Sign:* The Newest Vital Sign [21] is based on a nutrition label from an ice cream container. Participants are given the label and then asked 6 questions about it. Participants can refer to the label while answering questions. The questions are asked orally and the responses recorded by study staff on a special score sheet, which contains the correct answers. Based on the number of correct responses, the study staff can assess the patient's health literacy level.
 - c. *Modified Parental Health Literacy Activities Test (PHLAT):* The PHLAT [22] assesses parental health literacy and numeracy skills in understanding instructions for caring for young children.

3.5.3. Infant Formula Preparation

Participants will be asked to prepare a single 2 fl oz bottle of infant formula according to the manufacturer package instructions without assistance or interruption (**Figure 3**). Participants will be asked to prepare a 2 fl oz bottle again, but this time the weight of the dry powder scooped and the weight of the prepared formula will be recorded. Weights will be obtained (to the nearest tenth of a gram) using a METTLER TOLEDO PB3001 scale. Discrepancies between actual weight and the weight recommend by the manufacturer will be a point of discussion during the focus group. Both trials will be video recorded for future review by study staff to identify common points of error or confusion.

Figure 3: Commercially available instructions for preparation of infant formula

[figure not shown]
3.5.4. Focus Group Discussion

Focus group discussions will be led by a moderator who will follow a script of group discussion probes. During the focus group, participants will be asked to comment on discussion themes (e.g. attitudes towards infant feeding, current feeding practices, desired education regarding infant feeding, and recommendations to improve preparation instructions), and all responses will be audio and/or video tape-recorded and will be transcribed verbatim later. Responses will be de-identified in the transcript. Modified preparation instructions will be presented to the first focus group for discussion. The preparation instructions will be further modified based on participant feedback. Iterative focus groups will view and provide feedback on the preparation instructions modified by the previous focus group. Focus groups will continue until a satisfactory set of instructions are developed. Conducting focus groups in a stepwise fashion allow one focus group to build on the improvements recommended by another.

4. RESEARCH DESIGN: PHASE 2

Phase 2 is a randomized, controlled study to test the efficacy of the revised instructions on infant overfeeding in comparison with the instructions currently provided on the packaging (**Figure 4**). Individuals will be randomized in a 1:1 ratio to one of two groups:

1. **Group 1:** Group 1 participants will prepare infant formula following the standard infant formula preparation instructions provided by the manufacturer.
2. **Group 2:** Group 2 participants will prepare infant formula following the modified infant formula preparation instructions.

4.1. Study Population

Up to 150 individuals who did not participate in Whoa Baby Phase 1 will be recruited to participate in Whoa Baby Phase 2 at Pennington Biomedical Research Center.

4.1.1. Eligibility Criteria

Participants are eligible to participate in this study if they are:

- ≥18 years of age
- Did not participate in Whoa Baby Phase 1
- Willing to participate in 1 assessment visit at Pennington Biomedical Research Center
- English speaking

4.1.2. Exclusion Criteria

Participants are ineligible to participate in this study if they are:

- <18 years of age
- Did participate in Whoa Baby Phase 1
- Not willing to participate in 1 assessment visit at Pennington Biomedical Research Center
- Non-English speaking

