4.2. Recruitment

Potential participants will be recruited from within PBRC and the Greater Baton Rouge area via Institutional Review Board (IRB) approved posters, flyers and advertisements posted on the PBRC website (<http://www.pbrc.edu/clinicaltrials>) and through PBRC approved social media outlets including but not limited to Facebook, blogs, and Craigslist. In addition to recruitment in the community, the Reproductive Endocrinology and Women’s Health Laboratory has successfully recruited participants for pregnancy, breastfeeding, and women’s health studies through partnerships with Baton Rouge General and Ochsner OB/GYNs and local Women, Infants, and Children (WIC) clinics. Referrals from these collaborators will also be used in recruitment efforts.

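### Phase 2 bars only Phase 1 participants yet recruits inside the research centre, so staff or trainees who know of the over-scooping finding or the revised instructions can be randomised, which could dilute the arm difference

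*Combined protocol and SAP*

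**What the plan says.** The Phase 2 inclusion list (4.1.1) asks for age 18 or over, English speaking, willingness to attend one visit, and "Did not participate in Whoa Baby Phase 1". The exclusion list (4.1.2) mirrors it with "Did participate in Whoa Baby Phase 1". Neither list mentions employment at the centre, knowledge of earlier results, or participation in the Baby Bottle study.

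On sources, section 4.2 states: "Potential participants will be recruited from within PBRC and the Greater Baton Rouge area". Community advertising and referrals from obstetric practices and WIC clinics are also named.

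On what Phase 1 participants learn, section 3.5.3 says: "Discrepancies between actual weight and the weight recommend by the manufacturer will be a point of discussion during the focus group". Section 3.5.4 adds that they see and help to revise the modified instructions.

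On the earlier study, section 2.3 reports "we recruited 53 men and women aged 18-80 to prepare bottles of infant formula" at the same centre in 2012-2013, and "Of the 636 bottles prepared, 607 or 95% contained significantly more infant formula powder (by weight) than what was recommended on the package label".

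Screening (4.3) applies the basic criteria only. The Phase 2 interview (4.5.2) lists demographics, formula use, number of children and caregiver status as examples. It names neither staff status nor earlier study participation.

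**The concern.** Barring Phase 1 participants makes sense, because they have discussed the weight discrepancy and seen the sheet under test. The same reasoning reaches anyone at the centre who knows that scoops tend to be overfilled or has read the revised instructions. The finding arose there, the Phase 1 focus groups meet in its Demonstration Kitchen (3.4.1), and Phase 2 visits take place in the same kitchen (4.4.1).

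In the control arm, an informed person may scoop accurately for a reason unrelated to the manufacturer's sheet. In the new-instruction arm, the sheet may add little to what that person already knows. Either way, the person contributes less of a difference between arms than a naive participant would. At stake are an understated benefit and some loss of power. Because neither screening nor the interview is planned to capture this knowledge, it could not be reliably identified at analysis.

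**Working it through.** **Inputs from the plan.** Over-scooping 0.8 with the old instructions and 0.5 with the new (6.1 and Table 4); 75 per group (6.1); 1:1 allocation (section 4). Section 6.3 gives no value for alpha, so two-sided 0.05 is assumed.

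**Reproducing Table 4.** With the pooled-variance formula and no continuity correction,

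n = [1.96·√(2p̄(1−p̄)) + 0.842·√(p₁(1−p₁) + p₂(1−p₂))]² / (p₁−p₂)².

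For 0.8 vs 0.5: p̄ = 0.65, so n = [1.322 + 0.539]² / 0.09 = 38.5, rounded up to 39. The other rows give 294, 82 and 23. All four match the table, which supports the assumed alpha.

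**Power at the planned size.** Power = Φ{[d√75 − 1.96·√(2p̄(1−p̄))] / √(p₁(1−p₁) + p₂(1−p₂))}. For 0.8 vs 0.5 this is Φ[(2.598 − 1.322)/0.640] = Φ(1.99) = 97.7%.

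**Dilution.** Let f be the share of participants who already know of the error, and q their over-scooping rate, the same in both arms. Neither is in the documents; both are assumptions.

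- Control rate = 0.8(1−f) + qf
- New-instruction rate = 0.5(1−f) + qf
- Difference = 0.30(1−f), whatever q is

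Example with f = 20% and q = 0.5: control 0.74, new 0.50, difference 0.24. Power = Φ[(2.078 − 1.345)/0.665] = Φ(1.10) = 86.5%.

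| f | People of 150 | Difference | Power, q = 0.8 | Power, q = 0.5 | Power, q = 0 |
|---|---|---|---|---|---|
| 0 | 0 | 30 points | 97.7% | 97.7% | 97.7% |
| 5% | 7.5 | 28.5 | 96.4% | 96.1% | 95.6% |
| 10% | 15 | 27 | 94.6% | 93.8% | 92.7% |
| 20% | 30 | 24 | 89.1% | 86.5% | 84.4% |
| 30% | 45 | 21 | 80.4% | 75.4% | 73.8% |

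Power reaches 80% at f of about 30% (q = 0.8), 26% (q = 0.5) or 24% (q = 0), which is roughly 37 to 45 people of 150.

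**Sensitivity to multiplicity.** Section 6.3 tests each bottle size separately and leaves multiplicity adjustment open. If Bonferroni over four sizes were used (alpha 0.0125, an assumption), power per size would be 92% at f = 0, 81-85% at 10% and 68-75% at 20% over the same range of q. The margin is therefore narrower if the analysis is adjusted.

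**The case against.** The case for leaving the criteria alone is fair, and several parts of it stand.

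- **Practice.** A reader might infer that earlier bottle preparation, 12 bottles each in Baby Bottle (636/53), trains people out of the error. The protocol's own data point the other way. The error held across trials, leading section 2.3 to say "We can therefore assume that the unintentional over-scooping is consistent within an individual", and the same section reports that caregivers and non-caregivers did not differ.
- **Baby Bottle participants as an informed group.** A reader might count all 53 as aware, which would be 53/150 = 35% of the sample. The documents do not support this. That study was meant to validate a photography method, the summary (section 1) calls the over-scooping result unexpected, and nothing says participants were told their weights or saw any modified sheet. Nor is there any sign that they would all return.
- **Bias for one arm.** A reader might infer systematic bias in favour of one set of instructions. Allocation is randomised 1:1, so informed people are expected equally in both arms. If they behave alike under either sheet, the result is dilution toward no effect.
- **Staff numbers.** Section 4.2 does not mention employees, say how many might enrol, or say that they know the earlier result. The text permits their entry; it does not show that it would be common.

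What remains is narrower: the plan allows informed staff and trainees in and names no item that would identify them.

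**Conclusion.** The gap is real but minor. Phase 1 participation is the only prior-exposure bar, and people at the centre who know of the finding or the revised instructions are eligible as written. Their inclusion could shrink the arm difference; the documents do not show that it would.

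The size rests on two assumed quantities, the informed share and the absence of any arm difference among those people. For a share of 5% to 20%, the loss is 1.5 to 6 points of the planned 30, and power at unadjusted two-sided 0.05 stays between 96% and 84%. It drops below 80% only when roughly a quarter or more of the sample is unresponsive. These figures use the plan's basis of one binary outcome per participant and a single comparison. The case for acting rests on the low cost of the remedy and on the fact that an exclusion works only if it is in place before enrolment, not on any threat to the trial's validity.

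**What to change.** 1. Add one line to 4.1.2 excluding current staff or trainees of the centre who worked on Baby Bottle or Whoa Baby, or who know the results or the revised instructions of either. Check it with one webscreener question under 4.3.
2. As a low-cost precaution, also exclude earlier Baby Bottle participants, checked against the centre's own participant list. Alternatively, let them enrol, record the status at screening, and prespecify a sensitivity analysis that repeats the section 6.3 comparison without them.

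There is no need to bar every employee or to drop the centre as a recruitment source, because the line in item 1 targets knowledge and not employment as such. The cost is one or two eligibility lines, matching screening questions and a slightly smaller local pool. The community, obstetric and WIC routes in 4.2 are unaffected.

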4.2. Recruitment

Potential participants will be recruited from within PBRC and the Greater Baton Rouge area via Institutional Review Board (IRB) approved posters, flyers and advertisements posted on the PBRC website (<http://www.pbrc.edu/clinicaltrials>) and through PBRC approved social media outlets including but not limited to Facebook, blogs, and Craigslist. In addition to recruitment in the community, the Reproductive Endocrinology and Women’s Health Laboratory has successfully recruited participants for pregnancy, breastfeeding, and women’s health studies through partnerships with Baton Rouge General and Ochsner OB/GYNs and local Women, Infants, and Children (WIC) clinics. Referrals from these collaborators will also be used in recruitment efforts.

4.3. Study Screening

Interested participants will complete initial screening via phone or the online webscreener survey. Interested participants may contact study staff for study description and basic eligibility details via phone or email correspondence. Participants not meeting these basic criteria from the webscreener survey will be excluded. All eligible volunteers will be assigned a unique study ID number and referred to study staff for study specific screening and scheduling.

